Important note (3)	
A key point will be to understand the contribution of each of the drugs in generating toxicities. To this purpose, the CMC will specifically investigate whether observed toxicities relate to overlapping effects (such as fatigue, nausea diarrhea) or specific toxicities (such as febrile neutropenia – palbociclib) or low platelets level (axitinib). Appendix 8 describes all observed toxicities and outlines common or specific toxicities. Main toxicities specific to each drug are summarized in Important note (5).
 
Rules in case of toxicity/dose modifications:
 
For any Grade 3 dose-limiting toxicity (see page 32 for dose-limiting toxicity definitions) that is deemed to be drug specific, that drug will be held until resolution to <Grade 1. The drug will then be restarted with the dose at the next lowest level. If Grade 3 or greater toxicity recurs, the drug will be permanently stopped. Exception is hematologic toxicity which may be handled as in Important note (5), palbociclib section or Important note (6).
 
If a toxicity has been deemed to be due to a single drug, but persists at <math>\geq</math> grade 3 level after stopping the drug, all drugs will be stopped.
 
If it is unclear as to the drug that is causing a toxicity, all three drugs will be held.

	
Toxicities that may be clearly attributable to avelumab include immune toxicities such as immune mediated pneumonitis, hepatitis, colitis and nephritis, and infusion related reactions.
 
Toxicities clearly attributable to axitinib include hypertension and proteinuria.
 
Toxicities clearly attributable to palbociclib include lowering of white blood cells (WBC) or platelet counts.
 
For Grade 4 dose limiting toxicities, the drug to which it is attributable will be permanently stopped. If it is not clear as to which drug is associated with the toxicity, all drugs will be permanently stopped.
 
A Clinical Monitoring Committee (that includes site PIs) may be convened to help decide to which drug the toxicity is attributable.

Important note (4)	For dose interruption and reduction events, accurate medical administration records will be maintained to capture changes in dosing regimens, including concomitant medications.

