**Recurrent Grade 3 ADRs and Grade 3 infusion-related reaction require permanent discontinuation.**

**Any Grade 2 ADR should be managed as follows:**

- If a Grade 2 ADR resolves to Grade  $\leq$  1 by the last day of the current cycle, treatment may continue.
- If a Grade 2 ADR does not resolve to Grade  $\leq$  1 by the last day of the current cycle, infusions should not be given on the following cycle. If at the end of the following cycle the event has not resolved to Grade 1, it should be treated as a Grade 3 or 4 (except for hormone insufficiencies, that can be managed by replacement therapy; for these hormone insufficiencies, up to 2 subsequent doses may be omitted).
- Upon the second occurrence of the same Grade 2 ADR (except for hormone insufficiencies that can be managed by replacement therapy) in the same subject, treatment with avelumab has to be permanently discontinued.

Important note (6):	Specific protocol dose modification for toxicity management related to palbociclib: 

- In case of recurrent grade 3 hematologic toxicities, palbociclib may be reduced to 75 mg po daily one week off and one week on.

- In case of other severe (<math>\geq</math> grade 3) toxicity related to palbociclib, consider holding palbociclib until toxicity is grade 1 or less, then resume at the alternate schedule of 2 weeks OFF / 2 weeks ON.

----------------------------	---

- **DLT will be defined as:**

Any of the following events that are considered to be clinically significant and meaningful as per evaluation of the attending physicians and confirmed by CMC and at least possibly related to drug. DLTs for the purposes of dose-escalation will be evaluated during the 28-day period following the first dose of study treatment. Each treatment cycle is four weeks. Toxicities will be graded and documented according the NCI CTCAE (v4.03).

- **Non-hematological dose-limiting toxicity is defined as:**

- Persistent Grade 3 or 4 hypertension despite treatment with anti-hypertensive drugs.
- Grade 3 or 4 Gastrointestinal bleeding.
- Grade 3 or 4 Gastrointestinal perforation or fistula.
- Development of Reversible Posterior Leukoencephalopathy Syndrome.
- Persistent Grade 3 or 4 proteinuria.
- Grade 3 or 4 arterial or venous thromboembolic events.

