### 10.3. APPENDIX 3: Drug Information

- **Bavencio - avelumab:** has been approved in March 2017 for the treatment of metastatic Merkel Cell Carcinoma and in May 2017 for the treatment of locally advanced or metastatic urothelial carcinoma. Avelumab is an immune checkpoint inhibitor, directed against programmed cell death ligand 1 (PD-L1). Signals from PD-L1 help tumors avoid detection by the immune system. Avelumab blocks these signals, countering the tumor's immune-evading tactics. As an anti-PD-L1 antibody, avelumab binds to PD-L1, allowing T-cells to recognize and kill tumor cells. It exhibits no immunogenicity that impacts pharmacokinetics or pharmacodynamics at 10 mg/kg. The most common any-grade Adverse events (Aes) in patients receiving all doses of avelumab were fatigue (7%), nausea (5%), vomiting (5%), arthralgia (4%), and rash (4%).
- **Ibrance - palbociclib:** Approved in February 2015 for the treatment of ER positive HER2 negative breast cancers. Palbociclib is an orally available pyridopyrimidine derived cyclin dependent kinase inhibitor. Palbociclib is a very selective dual inhibitor of cyclin-dependent kinase (CDK) 4 and 6. It blocks progression of cells from G1 into S phase. In particular, it shows activity in presence of high levels of Cyclin A. MTD is 125 mg orally daily for 21 consecutive days, followed by 7 days off treatment. If the patient vomits or misses a dose, an additional dose should not be taken that day. The next prescribed dose should be taken at the usual time. Ibrance capsules should be swallowed whole (do not chew, crush or open them prior to swallowing). No capsule should be ingested if it is broken, cracked, or otherwise not intact. **Palbociclib capsules should be taken with food.** Grapefruit or grapefruit juice intake during the whole duration of the treatment should be avoided as it may increase concentration of the drug in blood. Most common adverse reactions (greater than or equal to 10%) is neutropenia, leukopenia, fatigue, anemia, upper respiratory infection, nausea, stomatitis, alopecia, diarrhea, thrombocytopenia, decreased appetite, vomiting, asthenia, peripheral neuropathy, and epistaxis. The most frequently reported serious adverse event were pulmonary embolism (4%) and severe diarrhea (2%). Avoid concomitant use of strong and moderate CYP3A inducers.).

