Gastrointestinal perforation and fistula	-	X	-	Specific	1% to 10%
Glossodynbia (burning mouth sensation)	-	X	-	Specific	1% to 10%
Haemorrhoids	-	X	-	Specific	1% to 10%
Hyperbilirubinemia	-	X	-	Specific	1% to 10%
Hypercalcaemia		X	-	Specific	1% to 10%
Polycythaemia	-	X	-	Specific	1% to 10%
Potassium and sodium increase	-	X	-	Specific	1% to 10%
Renal failure	-	X	-	Specific	1% to 10%
Tinnitus	-	X	-	Specific	1% to 10%
Venous embolic and thrombotic events and arterial embolic and thrombotic events	-	X	-	Specific	1% to 10%
Abdominal distension and discomfort	-	-	X	Specific	1% to 10%
Blurred vision, Lacrimation increase, Eye dryness	-	-	X	Specific	1% to 10%
Dry mouth	-	-	X	Specific	1% to 10%
Epistaxis (nose bleeding)	-	-	X	Specific	1% to 10%
Febrile neutropenia	-	-	X	Specific	1% to 10%
Hypoesthesia (reduced sense of touch or sensation)	-	-	X	Specific	1% to 10%
Hypotension	-	-	X	Specific	1% to 10%
Muscle spasms	-	-	X	Specific	1% to 10%
Muscular weakness	-	-	X	Specific	1% to 10%
Night sweats	-	-	X	Specific	1% to 10%
Pain and flank pain	-	-	X	Specific	1% to 10%
Palpitations	-	-	X	Specific	1% to 10%
Rhinorrhoea	-	-	X	Specific	1% to 10%
Adrenocortical insufficiency acute	X	-	-	Specific	0.1% to 0.99%
Acute hepatic failure, hepatic failure, hepatitis	X	-	-	Specific	0.1% to 0.99%
Anaphylactic reaction	X	-	-	Specific	0.1% to 0.99%
Autoimmune hepatitis	X	-	-	Specific	0.1% to 0.99%
Autoimmune hypothyroidism	X	-	-	Specific	0.1% to 0.99%
Blood creatinine phosphokinase increased	X	-	-	Specific	0.1% to 0.99%
Colitis (inflammation of the colon), autoimmune colitis and enterocolitis	X	-	-	Specific	0.1% to 0.99%
Dermatitis exfoliative	X	-	-	Specific	0.1% to 0.99%
Diabetes mellitus, type I diabetes mellitus	X	-	-	Specific	0.1% to 0.99%
Drug hypersensitivity, hypersensitivity and type I hypersensitivity	X	-	-	Specific	0.1% to 0.99%
Erythema multiforme	X	-	-	Specific	0.1% to 0.99%
Guillian-Barré syndrome	X	-	-	Specific	0.1% to 0.99%
Hypopituitarism	X	-	-	Specific	0.1% to 0.99%

Adverse Events	Avelumab	Axitinib	Palbociclib	Specificity	Frequency
Myositis (muscle inflammation)	X	-	-	Specific	0.1% to 0.99%
Pemphigoid	X	-	-	Specific	0.1% to 0.99%
Pruritus generalised	X	-	-	Specific	0.1% to 0.99%
Rash generalised, pruritic, erythematous, macular and popular	X	-	-	Specific	0.1% to 0.99%
Thyroiditis and autoimmune thyroiditis	X	-	-	Specific	0.1% to 0.99%
Tubulointerstitial nephritis	X	-	-	Specific	0.1% to 0.99%
Transaminase increased	X	-	-	Specific	0.1% to 0.99%

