Arthralgia (join pain)	X	X	X	Common to 3	More than 10% for Axitinib and for Avelumab, 1% to 10% for Palbociclib,
Headache	X	X	X	Common to 3	1% to 10% for Avelumab and Palbociclib, more than 10% for Axitinib
Rash	X	X	X	Common to 3	1% to 10% for Avelumab and Palbociclib, more than 10% for Axitinib
Weakness	X	X	X	Common to 3	1% to 10% for Avelumab and Palbociclib, more than 10% for Axitinib
Aspartate aminotransferase increased	X	X	X	Common to 3	0.1% to 0.99% Avelumab, 1% to 10% for Axitinib, more than 10% for Palbociclib

Adverse Events	Avelumab	Axitinib	Palbociclib	Specificity	Frequency
Blood alkaline phosphatase increased	X	X	X	Common to 3	1% to 10% for Avelumab and Axitinib, more than 10% for Palbociclib
Itching	X	X	X	Common to 3	1% to 10%
Myalgia (muscle pain)	X	X	X	Common to 3	1% to 10%

The following table lists serious adverse events (SAE) that may require hospitalization or may be irreversible, long-term, or life-threatening. This list contains also fatal events related to single drug treatment axitinib (total of 27 to date), palbociclib (total of 7 to date), avelumab (total of 5 to date).

*Adverse events and Serious adverse events are reported from trials with the drug administered as a single drug for all types of cancer and all origins, for treatment-related only (not all-causality) and all clinical phases.*

Serious Adverse Events	Avelumab	Axitinib	Palbociclib	Specificity
Acute liver failure, hepatitis and autoimmune hepatitis	X	-	-	Specific
Adrenal insufficiency	X	-	-	Specific
Anaemia	X	-	-	Specific
Anaphylactic reaction	X	-	-	Specific
Arthralgia	X	-	-	Specific
Ascites	X	-	-	Specific
Aspartate aminotransferase (AST) increased	X	-	-	Specific
Blood creatinine phosphokinase increased	X	-	-	Specific
Colitis (inflammation of the colon)	X	-	-	Specific
Constipation	X	-	-	Specific
Cough	X	-	-	Specific
Diabetes mellitus and Type 1 diabetes mellitus	X	-	-	Specific
Dyspnea	X	-	-	Specific
Edema peripheral	X	-	-	Specific
Guillain-Barré syndrome	X	-	-	Specific
hyponatramia	X	-	-	Specific
Hypothyroidism / hyperthyroidism / Thyroiditis	X	-	-	Specific
Infusion-related reaction	X	-	-	Specific
Myositis (muscle inflammation)	X	-	-	Specific
Non-cardiac chest pain	X	-	-	Specific
Pleural effusion	X	-	-	Specific
Rash generalised	X	-	-	Specific
Respiratory distress	X	-	-	Specific
Small intestinal obstruction	X	-	-	Specific
Transaminase increased	X	-	-	Specific
Tubulointerstitial nephritis	X	-	-	Specific
Type I hypersensitivity	X	-	-	Specific

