Serious Adverse Events	Avelumab	Axitinib	Palbociclib	Specificity
Weight decrease	X	-	-	Specific
Aorto-duodenal fistula	-	X	-	Specific
Arterial embolic and thrombotic events	-	X	-	Specific
Cerebrovascular accident	-	X	-	Specific
Circulatory collapse	-	X	-	Specific
General health degradation	-	X	-	Specific
Haemorrhage	-	X	-	Specific
Hepatic cancer	-	X	-	Specific
Hyperosmolar hyperglycaemic state	-	X	-	Specific
Hypertension	-	X	-	Specific
Metastatic renal cell carcinoma	-	X	-	Specific
Myocardial infarction	-	X	-	Specific
Pulmonary embolism	-	X	-	Specific
Venous embolic and thrombotic events	-	X	-	Specific
Weakness	-	X	-	Specific
Alveolitis allergic	-	-	X	Specific
Lung infection	-	-	X	Specific
Abdominal pain	X	X	-	Common to 2
Back pain	X	X	-	Common to 2
Decrease appetite	X	X	-	Common to 2
Dehydration	-	X	X	Common to 2
Dyspnoea (shortness of breath)	X	X	-	Common to 2
Fatigue	X	X	-	Common to 2
Haemoptysis (coughing up blood)	-	X	X	Common to 2
Hepatic failure	X	X	-	Common to 2
Intestinal perforation	-	X	X	Common to 2
Nausea	X	X	-	Common to 2
Pneumonia / Pneumonitis	X	-	X	Common to 2
Pyrexia (Fever)	X	X	-	Common to 2
Respiratory failure	X	-	X	Common to 2
Sepsis (general infection)	X	X	-	Common to 2
Syncope	-	X	X	Common to 2
Vomiting	X	X	-	Common to 2
Cardiac arrest	X	X	X	Common to 3
Diarrhoea	X	X	X	Common to 3

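### Appendix 8 lists pulmonary embolism as specific to axitinib while Appendix 3 reports it for palbociclib, so the table used to attribute toxicity may point to one drug only

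*Combined protocol and SAP*

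**What the plan says.** Appendix 8 (Section 10.8) has one column per drug, in the order avelumab, axitinib, palbociclib, and then a label saying whether the event is specific to one drug or shared. In the serious adverse event table the pulmonary embolism row reads "Pulmonary embolism - X - Specific". The broader venous row reads "Venous embolic and thrombotic events - X - Specific". The general adverse event table combines venous and arterial events: "Venous embolic and thrombotic events and arterial embolic and thrombotic events - X - Specific 1% to 10"%.

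A note in Appendix 8 gives the source of both tables: "Adverse events and Serious adverse events are reported from trials with the drug administered as a single drug for all types of cancer", and "for treatment-related only (not all-causality) and all clinical phases".

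Appendix 3 (Section 10.3), in the palbociclib entry, says: "The most frequently reported serious adverse event were pulmonary embolism (4%) and severe diarrhea (2"%). It does not say whether these rates come from palbociclib alone or in combination, or whether they count related events or all events.

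Important note (3) in Section 3.3.1 asks the CMC to separate overlapping from drug-specific toxicities. It refers to Appendix 8 as the document that "describes all observed toxicities and outlines common or specific toxicities". The DLT definition in the same section includes "Grade 3 or 4 arterial or venous thromboembolic events".

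**The concern.** Appendix 8 is more than background, because Important note (3) ties it to the question on which dose modification turns. A Grade 3 DLT deemed to come from one drug leads to that drug being held. A Grade 4 DLT leads to permanent stopping of the drug to which it is attributed. If the cause is unclear, all three drugs are affected. The dose-reduction paragraph in Section 3.3.1 likewise allows only the drug judged responsible to be reduced.

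For pulmonary embolism, then, the reference table offers a single candidate, while another appendix of the same protocol reports the event for a second drug given concurrently. A committee that consults Appendix 8 and not Appendix 3 has a written reason to treat the event as drug-specific. What is at stake is how an individual patient's drugs are modified after a potentially fatal event, and whether the trial's account of each drug's toxicity is right.

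**Working it through.** The point rests on no sample size, power or error rate, and the plan gives no figure to reproduce. The check is a side-by-side reading.

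**1. The two entries on pulmonary embolism**

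| Source | Avelumab | Axitinib | Palbociclib | Label |
|---|---|---|---|---|
| Appendix 8, serious events | blank | marked | blank | *Specific* |
| Appendix 3, palbociclib entry | – | – | 4% | none |

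Appendix 8 defines its common band as 1% to 10%, and 4% lies inside it. If the Appendix 3 figure were on the same basis as Appendix 8, palbociclib would be marked and the row would read *Common to 2*.

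**2. Control comparison.** The same Appendix 3 sentence names severe diarrhea at 2%. Appendix 8 marks serious diarrhoea for all three drugs. So of the two events in that sentence, one agrees with Appendix 8 and one does not.

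**3. Which rows are in conflict.** Appendix 3 names only pulmonary embolism. The pulmonary embolism row is therefore in direct conflict. The venous row, and the combined venous and arterial row, conflict only in so far as they include pulmonary embolism.

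**4. What other text could put the CMC on notice.** Section 1.1 links thromboembolic risk to axitinib and haematologic toxicity to palbociclib. Important note (5) places thromboembolic precautions under axitinib and has none under palbociclib. Among the passages compared, only the Appendix 3 drug summary names palbociclib for this event.

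**5. What depends on the attribution.** An event counts as a DLT if it is at least possibly related to study drug, whichever drug that is. The cohort rule in Important note (1) counts patients with a DLT. The toxicity boundaries in Section 7.3 do the same. Moving a pulmonary embolism from one drug to another changes none of these counts, so the MTD and RP2D do not move. What can change is modification within the patient (Important note (3) and the dose-reduction paragraph) and the assessment of each drug's contribution.

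**6. Other palbociclib rows (secondary).** Appendix 3 lists leukopenia, thrombocytopenia, peripheral neuropathy, alopecia and epistaxis among reactions seen in at least 10%. The first three have no row in the Appendix 8 adverse event table. The last two are there at 1% to 10%. That is five rows: three absent and two in a lower band.

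**The case against.** **The entries may not contradict each other.** Appendix 8 is limited to single-drug, treatment-related events. Section 1.1 describes palbociclib's approvals as combinations with letrozole or fulvestrant, so the 4% could come from combination or all-causality data. This stands as a possibility. The documents do not settle it, and the label may be correct for Appendix 8's own data. It does not remove the problem, because Important note (3) presents Appendix 8 as covering all observed toxicities and a reader cannot tell that the two sources differ. Appendix 8 does warn that further side effects may exist, but that warning concerns effects not yet known, and this one is reported in Appendix 3.

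**The protocol does not say that the label decides.** A reader might infer that a thromboembolic DLT must be attributed to axitinib while palbociclib continues. The documents do not support that. Important note (3) leaves attribution to judgement, with the CMC investigating. Its examples of toxicity clearly due to axitinib are hypertension and proteinuria; thromboembolism is not among them, although the list is open-ended. If the cause is unclear, all three drugs are held, or permanently stopped at Grade 4. If a toxicity attributed to one drug stays at Grade 3 or higher after that drug is stopped, all are stopped. This objection stands, and it is why the consequence is stated as possible and not as prescribed.

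**The frequency cannot be worked out.** A reader might multiply 4% by the number of patients to say how often the issue will arise. That is not supported. The 4% has no stated basis or exposure time, patients with a thromboembolic event within six months are excluded, the escalation DLT window is 28 days, and palbociclib is not given for the first seven of them.

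**The secondary rows matter less.** Important note (3) already names low white cell counts as clearly due to palbociclib, so the missing leukopenia row is unlikely to mislead. The two frequency differences may again reflect different sources, and the bands meet at 10%. This stands, so these rows are a tidying matter.

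**Conclusion.** The point holds in a limited form. Appendix 8 and Appendix 3 disagree on whether palbociclib is a reported source of pulmonary embolism, and Appendix 8 is the reference named for attributing toxicity. A CMC relying on it may attribute a thromboembolic DLT to axitinib alone.

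One row is in direct conflict, two more only in so far as they include the same event, and five palbociclib rows differ as a secondary matter. The possible effect is confined to dose modification within a patient and the assessment of drug contribution. A reader might infer that dose escalation is affected too; it is not, because DLTs are counted regardless of the causal drug. No probability can be attached.

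The conclusion assumes that the CMC uses Appendix 8 as Important note (3) describes. It does not assume that the Appendix 8 label is wrong, since the basis of the 4% is unstated. Because the event is serious and the correction cheap, it should be made. Nothing here says which drug should be held, reduced or stopped.

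**What to change.** Trace the source of the 4% in Appendix 3 and of the pulmonary embolism row in Appendix 8. State for each whether it is single-drug or combination data, and treatment-related or all-causality. Then reconcile Appendix 3 with the pulmonary embolism and venous rows of Appendix 8. Either the reference used under Important note (3) shows every drug for which the protocol reports pulmonary embolism, or a note beside the row explains why the entries differ. The result of the source check should decide between these; it should not be prejudged.

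In the same correction, check the palbociclib rows for leukopenia, thrombocytopenia, peripheral neuropathy, alopecia and epistaxis against Appendix 3.

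The cost is a source check and a text change to the appendices in a protocol amendment. It needs no additional patients, procedures or analyses.

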## 10.9. APPENDIX 9: Modulators of CYP3A4

### Relevant strong inhibitors and inducers of CYP3A4 list.

Strong CYP3A4 inhibitors or inducers are prohibited while on this protocol per [Important Note \(5\)](#). Moderate CYP3A4 inhibitors or inducers should be used with caution.

**\*Note:** This list is not exhaustive. It is expected that the patient's medications' list is reviewed by pharmacy to determine each medication potential effect on the CYP3A4 metabolism system. Medications that are used in disease states that are excluded by the SPRING protocol were specifically excluded from this list (HIV, hepatitis, etc.).

Modulators of CYP3A4	
Strong Inhibitors	Strong Inducers
Clarithromycin	Carbamazepine
Itraconazole	Fosphenytoin
Ketoconazole	Phenobarbital
Mifepristone	Phenytoin
Nefazodone	Primidone
Posaconazole	Rifampin
Suboxone	St John's wort
Telaprevir	
Telithromycin	
Voriconazole	

